### **14.5.3 New Information**

If new information becomes available that can significantly affect a subject's future health and medical care, then that information shall be provided to the subject(s) affected in written form. If relevant, all affected subjects shall be asked to confirm their continuing informed consent in writing.

### **14.6 Subject Information Card**

The subject will be provided with a Subject Information Card bearing the following information:

- That he/she is participating in a clinical trial (Trial Code: 000226).
- That he/she is treated with (AMPLEX or ABG).
- The name and phone number of the Investigator.
- Name and address of Ferring (if required by local regulations).

The subject will be asked to return the Subject Information Card at the last trial visit, if applicable.

#### **14.7 Compliance Reference Documents**

This clinical investigation shall be conducted in accordance with the ethical principles that have their origin in the Declaration of Helsinki, International Standard Organization (ISO 14155:2011) and any regional or national regulations.

The clinical investigation shall not begin until the required approval/favorable opinion from the IRB/REB or regulatory authority has been obtained, if appropriate.

Any additional requirements imposed by the IRB/REB or regulatory authority shall be followed.

## **15 LIABILITIES AND INSURANCE**

### **15.1 ICH-GCP Responsibilities**

The responsibilities of Ferring, the monitor and the Investigator are defined in the ICH-GCP consolidated guideline, and applicable regulatory requirements in the country where the trial takes place. The Investigator is responsible for adhering to the ICH-GCP responsibilities of investigators, for dispensing the investigational device in accordance with the approved protocol or an approved amendment, and for its secure storage and safe handling throughout the trial.

### **15.2 Liabilities and Insurance**

In case of any damage or injury occurring to a subject in association with the investigational device or the participation in the trial, Ferring has contracted an insurance which covers the liability of Ferring, the Investigator and other persons involved in the trial in compliance with the laws in the countries involved.

## **16 ARCHIVING**

### **16.1 Investigator File**

The Investigator is responsible for maintaining all the records, which enable the conduct of the trial at the site to be fully understood, in compliance with ICH-GCP. The trial documentation including all the relevant correspondence should be kept by the Investigator in accordance with investigative site and local regulatory requirement. All records shall, at a minimum, be retained for a period of time equivalent to the design and expected life of the device, but in no case less than 2 years from the date of release for commercial distribution by the manufacturer.

The Investigator is responsible for the completion and maintenance of the confidential subject identification code which provides the sole link between named subject source records and anonymous eCRF data for Ferring.

No trial site document may be destroyed without prior written agreement between the Investigator and Ferring. Should the Investigator elect to assign the trial documents to another party, or move them to another location, Ferring must be notified. If the Investigator retires and the documents can no longer be archived by the site, Ferring can arrange having the Investigator File archived at an external archive.

### **16.2 Trial Master File**

Ferring will archive the Trial Master File in accordance with ICH-GCP and applicable regulatory requirements.

## **18 APPENDICES**

## Appendix 1 Anticipated Adverse Events

Safety assessments involving AEs and SAEs are critical in the clinical assessment of new medical devices. Clinical trials evaluating medical devices often involve surgical or other procedures. As a result, AEs and SAEs can result from the medical device, the procedure itself, or the underlying medical condition. All AEs and SAEs will be reported regardless of cause. Nevertheless, since some AEs and SAEs impact on the primary efficacy assessment, Device-relatedness will be determined by the Investigator and adjudicated by the CEC. However, the relatedness of a number of AEs and SAEs are known. This table is provided as a guidance in assessing the better-known complications of arthrodesis surgery.

Adverse events associated with any surgical procedure could include:

### Likely:

- pain (not reported as an AE if related to graft site or harvest site)
- swelling
- adverse reaction to anesthesia including nausea, confusion, vomiting and elevations in liver enzymes

### Less Likely:

- soft tissue injury (swelling, warm to touch and/or pain to affected area)
- surgical site wound infection (drainage or pus at surgical site)
- cellulitis (inflammation of the soft tissue, especially below the skin characterized by fever, swelling, redness and pain)
- failure of the tissue to heal properly (wound breakdown or opening)
- other wound problem (fluid pocket formation)
- other infection (fever, aches and/or pain)
- hemorrhage (severe bleeding)
- nerve damage (weakness, tingling, and or numbness)
- muscular damage
- swelling, pain and/or redness at affected area
- arrhythmia (abnormal heart rhythm)

### Rare but serious:

- anesthesia complication (drug allergy, difficulty breathing, cardiac (heart) or systemic effect that could be life threatening)
- heart attack
- stroke
- pulmonary (lung) complications
  - pneumonia, (lung inflammation caused by infection)
  - atelectasis (shortness of breath caused by partial collapse of the lung)
  - respiratory distress (shortness of breath or respiratory failure)
  - pulmonary edema (excess water in the lung)
- pulmonary embolus (clogging of lung blood vessels by a blood clot)
- need for blood transfusion (risk of disease transmission)

- bad reaction to blood transfusion (fever, itching, heart failure or systemic illness)
- septicemia (life-threatening infection in the blood)
- seizures/convulsions
- changes in mental status
- death

Adverse events associated with foot/ankle fusion surgery include:

Likely:

- pain (evaluated as an efficacy assessment, not reported as an AE)
- swelling

Less likely:

- nerve injury (numbness sensation, tingling of affected area, decreased strength)
- adjacent joint degeneration (degeneration of the joint(s) next to the fusion at a later time requiring surgery)
- lack of pre-operative pain/symptoms reduction (signs and symptoms that were present before surgery remain the same after surgery)
- failure to achieve desired or any foot/ankle fusion (incomplete fusion of the bone)
- heavy surgical or post-surgical bleeding
- deep vein thrombosis (swelling or pain in the legs from a blood clot)
- paraesthesia (sensation of pricking, tingling and/or creeping on the skin)
- muscle and/or ligament injury

Rare but serious:

- fracture (bone breaks) of the tibia (leg), or bones of the foot
- osteolysis (resorption and/or dissolution of bone tissue)

Adverse events associated with foot/ankle instrumentation include:

Likely:

- pain and discomfort associated with implanted instrumentation (only if it can be differentiated from graft site pain)

Less Likely:

- misplaced, wrong sizing, loosened, broken or migrated implants (screws)
- implant displacement or migration (change of position)
- wear debris (accumulation of fragments)

Rare but serious:

- foreign body reaction to the implant (fever, swelling, and or discomfort)
- local or systemic allergic reaction (fever, aches and/or pain)
- damage to local structures

Adverse events associated with the study product include:

- Allergic reaction (local or systemic response)
- Ectopic bone growth (bone forming outside of normal bone growth areas)
- Abnormal cell growth (growth of tissue or cells beyond the norm)
- Negative effects on pregnancy or fetus
- Immune response (bodily response against foreign material)
- Significant increase in liver enzyme measures

Adverse events associated with harvesting autologous bone graft include:

- pain at the graft harvest site (evaluated as an efficacy assessment, not reported as an AE)
- swelling
- fracture at the graft harvest site
- soft tissue injury (swelling, warm to touch and/or pain to affected area)
- harvest site wound infection (drainage or pus at surgical site)
- cellulitis (inflammation of the soft tissue, especially below the skin characterized by fever, swelling, redness and pain)
- failure of the tissue to heal properly (wound breakdown or opening)
- other wound problem (fluid pocket formation)
- other infection (fever, aches and/or pain)
- hemorrhage (severe bleeding)
- nerve damage (weakness, tingling, and or numbness)
- muscular damage
- phlebitis thromboembolus (swelling, pain and/or redness at affected area)

**Appendix 2 Foot and Ankle Ability Measure Activities of Daily Living (FAAM-ADL)  
Questionnaire**

This document describes the planned statistical analyses for the AMPLEX pivotal study 000226 based on the Protocol Ver. 6.0 dated December 14, 2016.

1.1 Definitions/ Abbreviations

1.1.1 Definition of Terms

Terms	Definitions
Screened	Signed the informed consent form
Screen failed	Discontinued from the trial prior to randomization
Device	AMPLEX or ABG
Procedure	Index surgical fusion procedure or bone graft harvest procedure

1.1.2 Abbreviations

Abbreviations	Meaning of abbreviations in document
ABG	Autogenous bone graft
AE	Adverse event
ALP	Alkaline phosphatase
ALT	Alanine transaminase
ANCOVA	Analysis of covariance
AST	Aspartate aminotransferase
ATC	Anatomical therapeutic chemical
AUC	Area under the curve
BMI	Body mass index
BVF	Bone void filler
CEC	Clinical events committee
CI	Confidence interval
CT	Computerized tomography
DMC	Data monitoring committee
eCRF	Electronic case report form
FAAM-ADL	Foot and ankle ability measure; activities of daily living
FDA	Food and drug administration
IDE	Investigational device exemption
LOCF	Last observation carried forward
ITT	Intention to treat
MCS	Mental component summary
MedDRA	Medical dictionary for regulatory activities
mITT	Modified intention to treat
PCS	Physical component summary
PK	Pharmacokinetics
PP	Per protocol
PT	Preferred term
SAE	Serious adverse event

Abbreviations	Meaning of abbreviations in document
SAP	Statistical analysis plan
SF-12	Short form-12
SOC	System organ class
SPC	Subject performance composite
TEAE	Treatment-emergent AE
US	United States
VAS	Visual analog scale

2 Trial Objectives and Endpoints

2.1 Objectives

The primary objective of this pivotal study is to demonstrate that AMPLEX is non-inferior to ABG for bone fusion in a population indicated for single, double, or triple hindfoot arthrodesis or ankle arthrodesis surgery with supplemental graft material.

2.2 Endpoints

2.2.1 Primary Endpoint

The primary efficacy endpoint is the proportion of subjects who meet all the following criteria for the Subject Performance Composite (SPC) Endpoint at 52 weeks:

- Improvement in pain on weight-bearing at fusion site (≥ 20 mm reduction from baseline on 100 mm VAS)
- Absence of significant graft harvest site pain (< 20 mm on 100 mm VAS)
- Improvement in Foot and Ankle Ability Measure Activities of Daily Living subscale (FAAM-ADL) (≥ 8 points improvement from baseline)
- Absence of device related or procedure related SAEs (up to Week 52)
- Absence of secondary surgical or nonsurgical interventions intended to promote fusion (up to Week 52)

2.2.2 Key Secondary Endpoints

The key secondary endpoint is the proportion of subjects achieving CT radiographic fusion success at 52 weeks:

- Radiographic evidence of fusion by CT scan ($\geq 50\%$ bone bridging across the joint space for the full complement of joints in the absence of secondary surgical or nonsurgical interventions intended to promote fusion)

2.2.3 Other Secondary Endpoints

- Proportion of subjects achieving CT radiographic fusion success at 12 and 24 weeks (in the absence of secondary surgical or nonsurgical interventions intended to promote fusion)
- Change from baseline in pain on weight-bearing at fusion site at 12, 24, and 52 weeks (> 20 mm reduction from baseline on 100 mm VAS)
- ABG harvest site pain at 2, 6, 12, 24, and 52 weeks (< 20 mm on 100 mm VAS)
- Change from baseline in FAAM-ADL at 12, 24 and 52 weeks
- SPC at 12 and 24 weeks
- Change from baseline in Short Form-12 (SF-12) at 24 and 52 weeks

2.2.4 Safety Endpoints

- Frequency, severity and seriousness of Adverse Events (AEs)
- Device or Procedure Related SAEs
- Secondary surgical intervention including revision, removal, reoperation or supplemental fixation
- Subsidence, device migration, nonunion, osteolysis and/or heterotopic ossification in the area surrounding the implant site by radiographic assessment
- Presence of anti-B2A antibodies (Ab) in serum

2.2.5 Pharmacokinetic Endpoints

- Plasma B2A levels at Days 1, 2, 4, 7, and 15
- AUC, AUC_t, %AUC extrap, C_{max}, T_{max}, t_{1/2}, lamda z, CL/F, Vz/F for B2A

Note that the analysis of the pharmacokinetic (PK) endpoints are not in the scope of this SAP. The PK analysis will be performed by Translational Medicine Department, Ferring Pharmaceuticals A/S.

3 Trial Design

This is a prospective, multi-center clinical trial in subjects (≥ 18 and < 75 years of age) undergoing tibiotalar (ankle) arthrodesis or single, double, or triple hindfoot (talocalcaneal-, calcaneocuboid- or talonavicular-joint) arthrodesis with supplemental graft material and internal fixation with up to 3 screws per joint.

AMPLEX, the investigational device, is a synthetic bone graft substitute comprised of two parts; 1) a synthetic bone void filler (BVF) that functions as an osteoconductive scaffold and 2) a synthetic peptide (B2A) that augments osteodifferentiation. The control material, ABG, is harvested at the discretion of the surgeon from the calcaneus, proximal tibia, distal tibia or iliac crest and administered by surgical implant.

Prior to surgery, each subject will have baseline information collected which will include medical history, injury/disease etiology, diagnosis, clinical laboratory assessments (including serum for anti-B2A antibody analysis), pain and disability assessments, in addition to radiographic imaging.

As part of eligibility determination, the investigator will review any relevant diagnostic imaging results and comorbidities to ensure that subjects meet the appropriate eligibility criteria and that ankle or hindfoot arthrodesis surgery with supplemental graft material is indicated. Eligible subjects will be randomized as close to the procedure as possible, preferably on the day of the surgery.

Subjects will be randomly assigned on a two to one (2:1) basis to either the treatment group (AMPLEX) or the control group (ABG). Randomization will be stratified by clinical center, surgical site (hindfoot vs. ankle), and nonunion risk factors (none vs. any of: obesity, diabetes, previous hindfoot/ankle surgery, or smoking history). Permuted block randomization will be performed within strata. To minimize the opportunity for the sequence to be predicted, the block size will be variable.

Surgeries will be performed by board-certified/board eligible orthopedic surgeons. Perioperative prophylactic antibiotics will be administered before surgical incision in accordance with investigational site guidelines. Standard anesthesia procedures will be used. Standard surgical technique will be employed to gain access to each fusion site and to ensure rigid fixation of the fusion site. The joint will be exposed and prepared as per standard practice. The graft material should be placed in the joint space to minimize the chance of extrusion while maximizing bone-on-bone contact. Once the graft is placed, internal fixation screws will be placed across the joint. Up to three (3) screws can be used per joint. Supplemental pins and staples may be used, as well as supplemental screws and plates external to the fusion site(s). The surgical site will be closed in layers using standard surgical technique.

The trial is designed as a randomized, controlled trial comparing AMPLEX to ABG for bone fusion at 52 weeks. Although the primary efficacy endpoint will be assessed at 52 weeks, all subjects will be followed up for 78 weeks for the safety assessment. Post-discharge clinical visits will include

visits at 2, 6, 12, 24, 52 and 78 weeks. Adverse event data will be collected from randomization until the final follow up. The schedule of assessments is described in [Appendix 3](#).

3.1 General Design Considerations

Three independent parties will be established for endpoint assessment and safety monitoring.

An independent clinical events committee (CEC) will adjudicate device, procedural, or ancillary device related AEs, all events associated with secondary surgical interventions, and any other events specified in the CEC Charter.

An independent imaging core laboratory will centrally review all images. Osseous bridging will be assessed on a per-joint basis. The extent of osseous bridging will be semi-quantitatively scored (i.e., absent, <25%, ≥ 25 to <50 %, ≥ 50 to <75 %, and ≥ 75 to 100%) by assessing the area of bridged joint surface relative to the total area of joint surface available to be bridged (i.e., Bridged Surface Area/Total Surface Area = % Osseous Bridging).

An independent data monitoring committee (DMC) will periodically review clinical study data to ensure participants' safety, trial integrity, and scientific rigor. The DMC will develop and ratify a Charter that provides guidelines for oversight of trial safety.

3.2 Determination of Sample Size

Assuming true success rates of the primary endpoint to be 60% for ABG and 62% for AMPLEX groups, respectively, 396 subjects are needed to maintain 85% power to demonstrate non-inferiority of AMPLEX to ABG with a non-inferiority margin of -12% (AMPLEX minus ABG) at a type I error rate of 1-sided 5% in a 2:1 randomization (264 for AMPLEX and 132 for ABG). To maintain this sample size for the 78-week completers (per the FDA's recommendation) after taking account for approximately 15% discontinuation (including lost to follow-up) rate, a total of 480 subjects (320 for AMPLEX and 160 for ABG) will be randomized.

In this calculation, the true success rate for AMPLEX is assumed to be slightly higher than that for ABG because of the potential benefit for AMPLEX on the absence of significant graft harvest site pain component. The assumption on the true success rate for ABG is made based on the clinical endpoint results in DiGiovanni et al. (2013)¹ ([1](#)) and the Augment SSED (2015) ([4](#)). These data indicate relatively high success rates for each component at Week 52. The estimated success rate as a composite endpoint is approximately 60%, when it is assumed that the success of each component is independent of each other.

4 Subject Disposition

All subjects who signed the informed consent form will be considered screened for the trial. All screened subjects who discontinued from the trial prior to randomization will be classified as screening failures. Screening failures and their primary reason for screening failure will be tabulated. The number of screened subjects will be used as the denominator when the percentage of each primary reason for screening failure is calculated.

Subjects who were randomized, received the procedure (surgery), were treated with the graft material, prematurely discontinued from the study, and completed the study will be tabulated with the reason of premature discontinuations for all randomized subjects. Similar tabulations will be made by investigational site and by region (US or Canada).

The number and percentage of subjects who attended Visits 2, 3, 4, 5, 6, 7, and 8 will be tabulated for all randomized subjects based on the nominal visit data recorded on the eCRF.

The time from randomization to discontinuation will be summarized by the Kaplan-Meier method.

Subjects who discontinued from the trial after randomization will be listed by including information on the last visit attended. The list will be sorted by investigational site and subject ID.

5 Protocol Deviations

Subjects with important protocol deviations from the study conduct perspective will be tabulated and listed for all randomized subjects. The list will be sorted by investigational site and subject ID. The classification of important or non-important deviations will be completed by the sponsor and documented prior to the database lock.

The following protocol deviations will result in the exclusion of subjects for the per protocol (PP) analysis set:

- Deviations from the required pre-existing conditions that could affect the bone fusion
- Deviations from the procedural requirements that could affect the bone fusion or negatively impact the assessment of the bone fusion

Other unforeseeable types of protocol deviations may also result in the exclusion of subjects for the PP analysis set, and the final determination of those protocol deviations will be completed and documented prior to the database lock.

6 Analysis Sets

Subjects who are included and not included in each analysis set will be tabulated with the reason of the exclusion. The percentages will be calculated based on all randomized subjects. Subjects who are not included in each analysis set will be listed with the reason. The list will be sorted by investigational site and subject ID.

6.1 Intention-To-Treat Analysis Set

The intention-to-treat (ITT) analysis set will consist of all randomized subjects. Analyses for the ITT analysis set will be conducted according to the randomized treatment regardless of the actual treatment received.

6.2 Modified Intention-To-Treat Analysis Set

The modified ITT (mITT) analysis set will consist of all randomized subjects who have an attempted fusion of the index joints. If a subject becomes ineligible or withdraws prior to the initiation of surgery, the subject will not be included in the mITT analysis set. Once the surgery is initiated, all subjects will be included in the mITT analysis. Analyses for the mITT analysis set will be conducted according to the randomized treatment regardless of the actual treatment received.

6.3 Per Protocol Analysis Set

The per protocol (PP) analysis set will consist of all randomized subjects that: [1] complete the fusion procedure and receive either AMPLEX or ABG as assigned, [2] meet critical study eligibility criteria, and [3] have no significant protocol deviations (see Section 5).

6.4 Safety Analysis Set

The safety analysis set will consist of all treated subjects (i.e., received AMPLEX or ABG). Analyses for the safety analysis set will be conducted according to the actual treatment received.

7 Trial population

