## **9.4 Analysis Sets**

### **9.4.1 Modified Intention-to-Treat (mITT) Analysis Dataset**

The mITT analysis set will include all randomized subjects who have an attempted fusion of the index joint(s). If a subject becomes ineligible or withdraws prior to the initiation of surgery, the subject will not be included in the mITT analysis set. Once the surgery is initiated, all subjects will be included in the mITT analysis set.

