### **9.4.3 Safety Dataset**

The safety analysis set comprises all treated subjects and will be analyzed according to the actual treatment received.

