### **9.6.2 Primary Endpoint**

The primary efficacy endpoint will be the proportion of subjects who meet all of the following criteria for the SPC at 52 weeks:

- Improvement in pain on weight-bearing at fusion site ( $\geq 20$  mm reduction from baseline on 100 mm VAS)
- Absence of significant graft harvest site pain ( $< 20$  mm on 100 mm VAS)
- Improvement in Foot and Ankle Ability Measure Activities of Daily Living subscale (FAAM-ADL) ( $\geq 8$  points improvement from baseline)
- Absence of device related or procedure related SAEs (up to Week 52)
- Absence of secondary surgical or nonsurgical interventions intended to promote fusion (up to Week 52)

Non-inferiority of AMPLEX to ABG will be claimed if the lower bound of the 2-sided 90% CI for the difference of the proportions (AMPLEX minus ABG) is greater than -12.0%. The superiority will be claimed if the lower limit of the 2-sided 95% CI is greater than zero. The CI will be constructed with the normal approximation to the binomial.

The primary efficacy analysis will be based on the mITT analysis set. A sensitivity analysis will be conducted for the PP analysis set. In the analysis on the mITT analysis set, subjects who do not receive the assigned treatment will be analyzed as randomized.

For the primary analysis, the last observation carried forward (LOCF) approach will be used for subjects with missing SPC endpoint at 52 weeks. If there is no SPC endpoint assessment prior to 52 weeks, the subject will be considered not meeting the criteria.

The primary endpoint will also be analyzed for the subgroups defined by demographic characteristics, baseline comorbidities, rheumatoid arthritis, or surgical site. The treatment group comparisons after controlling each of these factors will be conducted by stratified analyses using the Mantel Haenszel method as sensitivity analyses

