### 9.9 Handling of Missing Data

For the primary and key secondary analyses, the imputation method of LOCF will be used in subjects with an unknown outcome.

Sensitivity analyses of missing data will be performed by utilizing the following imputation methods:

- 1) “missing-equals-failure”
- 2) multiple imputation methods

- 3) a tipping point analysis will be performed for the primary and key secondary efficacy endpoints which will allow assessment of sensitivity without need for postulating any missing data mechanism. For this analysis, all possible combinations of missing data from the two arms will be considered, and the point at which significance is no longer achieved will be identified.

The planned sensitivity analyses for the primary and key secondary endpoints will be described in further detail in the Statistical Analysis Plan (SAP).

All data collected on safety or adverse events will be reported to the extent it is available, regardless of the active/withdrawn status of participants.

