10.2 Adverse Events

Adverse events (AEs) will be classified according to the MedDRA version effective at trial start or later. The version of the MedDRA used for the final analyses will be documented.

A pre-treatment AE will be defined as an AE occurring before the initiation of the surgery. All AEs occurring after the initiation of the surgery will be considered treatment-emergent AEs (TEAEs).

If the timing of an AE cannot be established in relation to the initiation of the surgery, it will be considered as a treatment emergent AE.

Pre-treatment AEs will be reported in a listing only. This listing will be sorted by investigational site, subject ID and date of onset.

Any potential device, procedural, or ancillary device related AEs and all events associated with secondary surgical intervention will be adjudicated for the severity and relatedness by the Clinical Events Committee (CEC). The type of the secondary surgical intervention will also be adjudicated. In the adverse event summaries, the adjudicated data will be used for those events.

The relationship to device (i.e., graft material), ancillary device, index surgical fusion procedure, or bone graft harvest procedure will be evaluated as definitely, probably, possibly, unlikely, unrelated, or unknown. Any events evaluated as definitely, probably, possibly, or unknown will be classified as related.

Device related AEs will include all AEs classified as related to the graft material. Procedure related AEs will include all AEs classified as related to the index surgical fusion procedure or the bone graft harvest procedure.

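### The safety set starts at receipt of graft, but mITT entry and treatment-emergence start at surgery, so adverse events in subjects operated on without graft reach no AE summary table

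*SAP*

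**What the plan says.** **Safety set.** SAP 6.4: "The safety analysis set will consist of all treated subjects (i.e., received AMPLEX or ABG". It adds: "Analyses for the safety analysis set will be conducted according to the actual treatment received". Protocol 9.4.3 is looser: "The safety analysis set comprises all treated subjects and will be analyzed according to the actual treatment received". The protocol does not define treated there; the firm requirement of graft receipt comes from the parenthesis in the SAP.

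**Primary efficacy set.** SAP 6.2: "Once the surgery is initiated, all subjects will be included in the mITT analysis". Protocol 9.4.1 agrees: "Once the surgery is initiated, all subjects will be included in the mITT analysis set". Protocol 9.6.2 confirms its role: "The primary efficacy analysis will be based on the mITT analysis set".

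**Treatment-emergence.** SAP 10.2: "All AEs occurring after the initiation of the surgery will be considered treatment-emergent AEs (TEAEs". Protocol 9.7.2 also takes the start of surgery as the starting point.

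**Where safety is evaluated.** SAP 10.1 evaluates safety parameters on the safety set and reports them by graft material actually received. Protocol 9.7.1 and 9.7.2 use the same set.

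**Procedure.** SAP 1.1.1 counts the bone graft harvest, as well as the index fusion, as procedure.

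**The concern.** Two clocks start when surgery starts; the third starts only when graft is received. Between them lies a subject whose operation was begun and who left theatre with neither AMPLEX nor ABG. That subject counts in the primary analysis and can have treatment-emergent events, yet is outside the only population in which such events are tabulated.

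The plan itself allows for the case. SAP 4 counts subjects who had surgery separately from those treated with graft. Protocol 5.5.1 provides for AMPLEX that is prepared but not implanted, and allows a replacement only if time permits.

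Device- or procedure-related SAEs are a named safety endpoint and a component of the primary endpoint. Harvest-site fracture and haemorrhage are anticipated events in Protocol Appendix 1. Only the ABG arm has a harvest step, so losing events of that kind would make the ABG safety profile alone look better than it was.

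**Working it through.** **Tracing one subject.** Take an ABG subject whose harvest and index operation are begun, who has a serious harvest-site bleed, and in whom no graft is placed.

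1. mITT (SAP 6.2): in, because surgery was initiated.
2. Event timing (SAP 10.2): treatment-emergent, because it follows initiation of surgery.
3. Safety set (SAP 6.4): out, because neither AMPLEX nor ABG was received.
4. AE overview and incidence tables (SAP 10.2.1, 10.2.2): not counted, because SAP 10.1 fixes the population. It makes no exception for the supporting listings.
5. Pre-treatment AE listing (SAP 10.2): not there, because that listing covers only events before surgery starts.
6. Listing of exclusions (SAP 6): the subject appears with a reason for exclusion, but without the events.
7. SPC component summary (SAP 9.2.1): possible, since the absence of related SAEs is a component. SAP 9.2.1 assesses it up to the date of the visit-based measures. If the subject leaves before any such visit, the plan gives no assessment period, and the subject is a failure under the no-data rule whatever the SAE status.

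No other text assigns the subject to a safety arm or provides an output for the events.

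**Size.** The plan states no figure on this point. From the documents: 480 randomised (320 AMPLEX, 160 ABG). Everything else is assumed: a rate r of operations stopped before implantation, a procedure-related SAE rate s over all operated subjects, and the fraction f of stopped subjects who have such an SAE. Using 480 as the number of operations slightly overstates it if some subjects withdraw before surgery.

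- Subjects affected = 480 × r. At r = 0.5%: 2.4 (0.8 in ABG). At r = 1%: 4.8 (1.6 in ABG).
- Chance of at least one = 1 − (1 − r)^480. At r = 0.5%: 91%. At r = 1%: 99%.
- Share of subjects with a procedure-related SAE who are lost = (480 × r × f) / (480 × s).

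| f | s | r = 0.5% | r = 1% |
|---|---|---|---|
| 0 | any | 0% | 0% |
| 0.5 | 5% (24 subjects) | 1.2/24 = 5% | 2.4/24 = 10% |
| 1 | 5% (24 subjects) | 2.4/24 = 10% | 4.8/24 = 20% |
| 1 | 10% (48 subjects) | 2.4/48 = 5% | 4.8/48 = 10% |

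**Illustration in the ABG arm.** Suppose 8 grafted subjects and 2 ungrafted subjects had a procedure-related SAE. The safety table would show 8/158 = 5.1%; all operated subjects give 10/160 = 6.3%.

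**Effect on the primary test.** None. The planned 264/132 can be reproduced: the standard error is √(0.62×0.38/264 + 0.60×0.40/132) = 0.0521, and (0.12 + 0.02)/0.0521 − 1.645 = 1.04, which gives 85.2% power against the stated 85%. Nothing here changes that calculation or the type I error.

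**The case against.** **Protocol 9.9 already covers it.** It says: "All data collected on safety or adverse events will be reported to the extent it is available, regardless of the active/withdrawn status of participants". A reader might infer that the SAP flatly contradicts this. It does not: the sentence concerns subjects who remain in or leave the study, not subjects without graft, and it defines no population. By the same token it does not close the gap, because it names no table. What stands is that the SAP does not carry out this general intent for these subjects.

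**The subjects do not vanish.** This is true. Disposition counts them, the exclusion listing names them, SAEs are reported to the sponsor within 24 hours, and the CEC adjudicates potentially related events. A related SAE may also show in the SPC component summary, so a claim that the events appear nowhere would go too far. But that summary is an efficacy output, and it omits unrelated and non-serious events.

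**The numbers are conjecture.** A reader might infer that one in five procedure-related SAEs would be missing. That figure is the top of the range. It needs a 1% stop rate, a 5% SAE rate and an SAE in every stopped subject. The documents do not say that stopped operations are enriched for serious events, plausible as that is. The finding rests on the rules.

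**Anaesthetic events.** An event before surgery starts is a pre-treatment AE and is listed, so it is not part of this gap. SAP 7.4.1 times the procedure from first incision.

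**A harvest-only start may not be an attempt at fusion.** The first sentence of SAP 6.2 leaves some doubt. The later sentence makes initiation of surgery decisive, and SAP 1.1.1 treats harvest as procedure. The remaining doubt is a reason to spell it out.

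**Safety and efficacy outputs would differ anyway.** This is correct. The SPC runs to Week 52 by randomised arm, and safety runs to Week 78 by material received. Full reconciliation is therefore not an argument for the change.

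**Conclusion.** The concern holds as a mismatch of stated rules. A subject with surgery initiated but no graft received is in the mITT set, can have treatment-emergent events, and is outside the population for every AE summary table. Few subjects are likely to be involved: about 2 to 5 if 0.5% to 1% of 480 operations are stopped. The loss of procedure-related SAEs lies between none and an upper bound of about 10% to 20%, on the assumptions shown. Safety is descriptive, so no test is affected.

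A reader might also infer that the plan fails because it has no rule for a subject given both materials. That is a separate matter of convention. The documents describe one assigned material per subject, and this point does not rest on it.

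The change should be made before database lock, because a pivotal trial's SAE tables should include events from operations that were begun and abandoned.

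**What to change.** In SAP 6.4 and Protocol 9.4.3, define the safety set as all randomised subjects in whom surgery, meaning the index fusion or the harvest procedure, was initiated. Use the same initiation-of-surgery trigger as the mITT set and the treatment-emergent definition. Do not use anaesthesia, which could admit subjects who have only pre-treatment events and are not in the mITT set. Analyse by graft material received; if none was received, analyse by randomised arm with a flag. The same fallback would settle where an ungrafted subject goes in the as-treated sensitivity analysis of SAP 9.2.2, which is run on the mITT set.

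The minimum alternative is to keep the present set and add one table and one listing, by randomised arm, of treatment-emergent events in subjects with surgery initiated and no graft received.

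The cost is a sentence or two in each document, with no new data collection and no effect on sample size or error rates. The one drawback is that a few subjects without graft exposure enter the safety denominators; the flag makes them visible.
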